8.3.1 Safety Analysis

All safety analyses will be performed using the Safety Population.

AEs including changes in laboratory values will be graded according to the National Cancer Institute's *Common Terminology Criteria for Adverse Events Version (CTCAE) 4.0* (<http://ctep.cancer.gov/reporting/ctc.html>). The frequency of AEs will be summarized by system organ class, preferred term, severity (grade), and relationship to study treatment. For each of these summaries, subjects will be counted at most once within each organ class or

preferred term at the greatest severity. For these summaries, relationship to study treatment will be categorized as either treatment related (possibly, probably, or definitely related to study medication) or unrelated. Similar analyses will be performed for SAEs.

For all reported adverse events and SAEs, the risk of the event in each arm will be described using event rates and an analysis based on a Poisson regression model will be conducted to compare the rate of each type of event in the treatment groups. The proportion of subjects experiencing at least one event will be reported and the treatment groups compared based on Fisher's Exact Test.

Treatment-related mortality, defined as death occurring at any time after randomization and possibly, probably, or definitely resulting from study treatment, and all-cause mortality, defined as any death occurring after randomization, will be summarized. The proportion of subjects dying in each treatment group will be reported and the treatment groups compared based on Fisher's Exact Test.

Laboratory parameters will be summarized both overall and by treatment group using appropriate descriptive statistics. For quantitative safety parameters, change from the last pre-randomization assessment to the final visit assessment will be summarized overall and by treatment group. For qualitative parameters, descriptive information on shifts in pre- to post-randomization findings will be provided. In addition, abnormal and clinically significant abnormalities will be summarized and listed separately.

All safety comparisons and associated p-values are considered exploratory, not as formal tests of hypothesis. As such no adjustments will be made for multiple comparisons and all p-values must be interpreted cautiously.

Detailed listings of AEs, deaths, and safety-related laboratory values will be generated as specified in the Statistical Analysis Plan (SAP).

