8.4.2 Interim Analysis of Safety Data

The DSMB will periodically review safety data as described in Section 7.8.2, *DSMB Review*. The safety analyses for this trial will be descriptive rather than inferential. Detailed listings and summary tabulations of adverse events and safety-related laboratory values will be generated as specified in the Statistical Analysis Plan. The safety analyses will be completed using the safety population without stratification.

No formal stopping rules for safety endpoints are specified.

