- All NCI-CTCAE Grade 3-5 AEs, which are defined as possibly, probably, or definitely related to rituximab
- All NCI-CTCAE Grade 3-5 adverse events

- All infection related AEs

In addition, AEs classified by MedDRA SOC and preferred term will be summarized for each treatment group and overall for each of the following:

- All AEs
- AEs by maximum severity
- AEs by relationship to study drug: relationship to study treatment will be categorized as either treatment related (possibly, probably, or definitely related to study medication) or unrelated
- All infection related AEs

Summary tables will present the total number of events as well as the number and percentage of subjects experiencing the events. If a subject experiences the same AE on multiple occasions, the event will be counted once for each occurrence when reporting the number of AEs. When reporting the number of subjects experiencing the events, a subject will only be counted once if they experience an event within the particular SOC or preferred term. Percentages will be based on the number of subjects in the safety population.

AEs classified by MedDRA system organ class and preferred term will be summarized for each treatment group and overall, and incidence rates for AEs classified by MedDRA SOC and preferred term will be provided for each treatment group and overall. The incidence rate for a SOC or preferred term will be defined as the number of AEs divided by the person-time of exposure aggregated in each treatment group, and an analysis based on a Poisson regression model will be conducted to compare the rate of each type of event in the treatment groups. The proportion of subjects in each study arm experiencing each type of AE will be compared using a Fisher's Exact test.

Separate data listings will be provided for the following subsets:

- Treatment-related AEs
- AEs leading to study drug discontinuation
- Grade 3-5 AEs which are defined as possibly, probably, or definitely related to rituximab
- All Grade 3-5 AEs
- Infections
- Grade 3 and higher infections that occurred during the quarterly monitoring period
- AEs occurring from informed consent and prior to treatment initiation

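### Adverse event rates are compared by Poisson regression on repeat events with no stated allowance for clustering within subjects, so p-values for frequent categories may be too small

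*SAP*

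**What the plan says.** SAP 8.2 (Adverse Events) sets three rules that work together. For a subject who has the same AE more than once, "the event will be counted once for each occurrence when reporting the number of AEs". The incidence rate for a system organ class or preferred term is "the number of AEs divided by the person-time of exposure aggregated in each treatment group". For the comparison of arms, "an analysis based on a Poisson regression model will be conducted to compare the rate of each type of event in the treatment groups". Protocol 8.3.1 (Safety Analysis) has the same plan for AEs and SAEs: "an analysis based on a Poisson regression model will be conducted to compare the rate of each type of event". Neither section names a variance estimator, a dispersion scale or a term for the subject.

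SAP 8.2 also plans a second, subject-level comparison: "The proportion of subjects in each study arm experiencing each type of AE will be compared" by Fisher's exact test. Protocol 8.3.1 sets the status of all these results: "All safety comparisons and associated p-values are considered exploratory, not as formal tests of hypothesis".

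SAP 7.3.7 handles another repeat-count outcome, new digital ulcers, with a marginal Poisson model fitted by GEE with a within-subject working correlation. The AE section has no counterpart to this.

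**The concern.** Ordinary Poisson regression takes the variance of a count to equal its mean. That fails if some subjects have many events and others few. This trial gives reason to expect such differences: it enrols NYHA classes II to IV (Protocol 4.1), background PAH therapy ranges from one agent to combinations (Protocol 5.7.1), and concurrent immunosuppressants are optional (Protocol 5.7.2). The model would then treat repeat events in one subject as independent information. Its standard errors would be too small and its p-values too low.

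At stake is whether a rate difference reported for a B-cell-depleting drug in 60 subjects can be read at face value. A few event-prone subjects in one arm could produce an apparent excess, or an apparent protective effect.

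**Working it through.** **No figure to reproduce.** The documents state no AE rate, dispersion, standard error or error rate for this comparison.

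**Inputs from the documents.** 30 subjects per arm (Sample Size, synopsis); follow-up to Week 48 (Protocol 3.3.1); 20% drop-out (Protocol 8.1, a sample-size assumption, used here for exposure time).

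**Assumptions.** A two-sided 0.05 level, which the SAP states only for the primary endpoint. Mean events per subject μ from 0.1 to 6 over full follow-up, and dispersion k from 0 to 2, with variance μ + kμ².

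**Step 1, formula.** Let φ be the variance-to-mean ratio. The ordinary Poisson standard error is 1/√φ of the true one, so the large-sample type I error is 2 × [1 − Φ(1.96/√φ)].

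- φ = 1: ratio 1.00, error 5.0%
- φ = 1.5: ratio 0.82, error 11.0%
- φ = 2: ratio 0.71, error 16.6%
- φ = 3: ratio 0.58, error 25.8%

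**Step 2, simulation with no true difference.** Gamma-Poisson counts, 20% of subjects leaving at uniform times, 20,000 trials per cell. The columns give ordinary Poisson Wald error, mean estimated φ, and error with a robust (sandwich) or Pearson-scaled variance.

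| μ | k | φ | Poisson | Robust | Scaled |
|---|---|---|---|---|---|
| 0.1 | 0.5 | 1.03 | 0.2% | 0.2% | 0.3% |
| 0.1 | 1 | 1.08 | 0.3% | 0.2% | 0.3% |
| 0.3 | 0.5 | 1.12 | 4.7% | 3.8% | 3.8% |
| 0.3 | 1 | 1.23 | 6.4% | 4.4% | 3.9% |
| 1 | 0.5 | 1.43 | 10.5% | 5.5% | 5.3% |
| 1 | 1 | 1.84 | 15.5% | 5.8% | 5.2% |
| 3 | 0.5 | 2.31 | 20.5% | 5.3% | 5.3% |
| 3 | 1 | 3.57 | 31.6% | 5.8% | 5.6% |

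With no overdispersion (k = 0) the ordinary Poisson error is 0.2% to 5.0%. With k = 2 it is 8.8% at μ = 0.3, 24.6% at μ = 1 and 44.4% at μ = 3.

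**Step 3, cross-check.** Putting the simulated φ into the formula gives 10.1% and 14.9% at μ = 1, and 19.7% and 30.0% at μ = 3. These are close to the simulated values. At μ = 0.3 and below, the Wald test falls under the formula because counts are sparse.

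**Step 4, the remedy and the parallel test.** Over k = 0 to 2 and μ of 0.3 or more, robust variance gives 3.4% to 6.9% and Pearson scaling 3.5% to 6.0%. At μ = 0.1 both are below 0.5%, so neither helps there. A likelihood-ratio Poisson test at μ = 0.1 gives 8.4% even with k = 0, which is a sparse-count effect and not clustering. Fisher's exact test on subjects with any event is at most 3.1% in every scenario.

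**The case against.** Four points can be made for the plan.

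**The SAP does not exclude a robust or scaled variance.** This is true. A reader might infer that the sponsor chose the uncorrected variance; the documents are only silent. Read as written, though, the text describes ordinary Poisson regression, and the contrast with SAP 7.3.7 makes the omission visible. One sentence is needed either way.

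**The rates that matter may be low.** SAP 8.2 compares each type of event and collects only grade 2 and above. Protocol 1.4 reports infections in 39% of rituximab-treated RA patients, which under a Poisson model is −ln(1 − 0.39) ≈ 0.5 per subject, in another population. The review trigger in Protocol 7.8.2(d) is 0.2 related events per subject, though that is a threshold and not an expected rate. With dispersion 0.5 to 1.0, ordinary Poisson error is about 3% at a mean of 0.2 and about 7-10% at 0.5. This stands: the large inflation needs frequent categories.

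**No formal conclusion rests on these tests.** Protocol 8.3.1 adds that "no adjustments will be made for multiple comparisons and all p-values must be interpreted cautiously", and for interim review Protocol 8.4.2 says "The safety analyses for this trial will be descriptive rather than inferential". The DSMB triggers use counts and ratios, and mortality is compared by Fisher's exact test and log-rank. This limits the harm but does not remove it: a descriptive p-value is useful only if roughly calibrated, and general caution does not tell a reader how far to discount it.

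**Fisher's exact test is valid with repeat events.** It is, but it asks whether a subject had any event, so it does not calibrate the rate comparison.

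**Conclusion.** The point holds in a limited form. Repeat events enter a Poisson comparison with no stated allowance for clustering. If subjects differ in event propensity, p-values for frequent categories will be too low. Under assumed dispersion of 0.5 to 1.0 and 30 per arm, type I error is about 5-6% at a mean of 0.3 events per subject, 10-16% at 1 and 20-32% at 3. Rare preferred terms are not inflated under the Wald test. The sizes depend on event rates and dispersion that the documents do not give.

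A reader might go further and infer that false differences will be common, or that these comparisons are the trial's main safety evidence. The documents support neither: the first needs unstated rates, and the second ignores the parallel Fisher's tests and the exploratory status of safety p-values. Nor can one say that reported confidence intervals will be too narrow, because none is specified for AE rate comparisons. The consequence is miscalibrated descriptive rate comparisons, with no effect on the primary endpoint.

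**What to change.** In SAP 8.2, state that AE rates are compared by a Poisson model fitted to one count per subject, with ln(person-time) as offset and a robust (sandwich) or Pearson-scaled variance. This accords with the GEE approach in SAP 7.3.7. Subject-level data are essential, since arm totals alone carry no information on variation between subjects. State also that Fisher's exact test is relied on for sparse terms, with a minimum event count below which the rate model is not fitted. A negative binomial model is another candidate, but its error rate was not checked here.

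The cost is a sentence or two and one option in the model, with no new data. Rate comparisons in frequent categories will have somewhat larger p-values.

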8.3. Deaths and Serious Adverse Events

8.3.1. Serious Adverse Events

Serious adverse events (SAEs) and events requiring 24-hour reporting to the sponsor will be summarized by MedDRA SOC and preferred term in a manner analogous to what is described in Section 8.3. SAE summary tables by MedDRA SOC and preferred term will be provided by severity and relationship to study therapy as well.

8.3.2. Deaths

Any death that occurs while a subject is active in the main study (up to Week 48) will be collected and reported as a SAE, and any death that occurs after main study completion will only be reported as a SAE if the subject is active in quarterly monitoring for B cells and if the cause of death is determined to be a Grade 3 or higher infection. Additionally, an assessment of vital status approximately two years post randomization will be conducted via telephone or

review of public records or health registries (to which the subject has consented to share this data). Any deaths discovered from this review will be recorded on the Post-Study Follow-Up/ Week 104 Vital Status CRF page.

Treatment-related mortality will be defined as death occurring after randomization and before Week 48, and possibly, probably, or definitely resulting from study treatment. Treatment-related mortality can only be assessed if a death was reported as a SAE; relationship to study treatment was not collected for deaths recorded on the Post-Study Follow-Up/ Week 104 Vital Status CRF page. As such, treatment-related mortality will be summarized at Week 48.

All-cause mortality, defined as any death occurring after randomization, will be summarized at Week 48 and Week 104.

In addition, time to all-cause mortality will be defined as the number of months post-randomization until death from any cause. If death does not occur during the post-randomization study period (up to Week 104), then time to all-cause mortality will be set equal to Week 104 or the day of the Week 104 vital status telephone call, whichever occurred first. Appropriate censor variables will be defined to indicate whether the time-to variables represent event times or a censor times. Kaplan-Meier survival curves from each treatment arm will be compared using the log-rank test.

Separate displays listing and summarizing death, including time to death and cause of death, will also be created

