The clinical manifestations of SSc include Raynaud phenomenon and skin fibrosis and, in its severest form, sclerosis of multiple internal organs with vascular inflammatory and fibrotic components. Of the numerous manifestations that affect multiple organ systems, pulmonary involvement produces some of the most common and serious complications of the disease. The major pulmonary manifestations of SSc are interstitial lung disease and systemic sclerosis-associated pulmonary arterial hypertension (SSc-PAH). Estimates of the prevalence of PAH in patients with SSc have varied widely based on the definition of PAH and the method of obtaining the measurements (i.e. cardiac catheterization or echocardiography) but is thought to be between 8 and 12%. A conservative estimate of PAH prevalence of 10% among patients with SSc in the United States would indicate a prevalence of 24 individuals per million, which may actually be higher than the number of patients affected by idiopathic PAH. Further, patients with SSc-PAH tend to have a worse prognosis compared to all other forms of PAH. One year survival rates for SSc-PAH patients range from 50-81%, which is considerably lower than the 88% one year survival rate for idiopathic PAH patients [3-5]. One study documented survival rates for individuals with SSc-PAH of 81%, 63% and 56% at 1, 2, and 3 years from diagnosis respectively [4]. A more recent study again suggested a 3-year survival rate of 52% in patients with SSc-PAH [6].

SSc-PAH assumes three basic forms: 1) severe SSc-PAH accompanying limited cutaneous SSc, 2) SSc-PAH accompanying (secondary to) interstitial lung disease, and 3) a more indolent form of SSc-PAH which reflects vascular pathology of SSc [7]. Although there appear to be different subtypes of SSc-PAH, it is not known if and how the pathogenesis differs with each form. In all patients with SSc, SSc-PAH significantly worsens survival and is the leading cause of mortality in these patients.

Treatment for this disease is currently limited to the same vasodilator therapy employed in all forms of PAH. An evaluation of 91 patients with PAH treated with prostanoids revealed that

SSc-PAH patients had the worst survival of all subgroups analyzed [8]. SSc-PAH is a life-threatening illness for which there is currently no cure.

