The implications of these observed events call for further discussion. For example, determining the effect of rituximab on infections is problematic since patients treated with rituximab often have concomitant immunodeficiency and/or are on immunosuppressive drugs. In patients treated for B cell lymphomas, the incidence of serious infections (grade III or IV including sepsis) is about 2%. One reassuring finding has been the observation in several studies that total serum IgG and levels of protective IgG antibodies are generally maintained after treatment with rituximab [117, 118]. Cases of hypogammaglobulinemia have been reported [119-122]. Criteria supporting the use of IVIG should probably be similar to those used for other patients with secondary humoral immunodeficiency, for example: (i) low levels of protective antibodies to encapsulated organisms, viruses, or bacterial toxins without a response to immunization; (ii) severe hypogammaglobulinemia (serum IgG < 200 mg/dL); and (iii) increased rate, severity, or duration of infections, especially infections of the respiratory system or with encapsulated organisms including, but not limited to, *Streptococcus pneumoniae*, *Haemophilus influenzae*, and *Neisseria meningitides* [123, 124].

Serious viral infections, either new, reactivated, or exacerbated, have been reported after use of rituximab including CMV, herpes simplex virus, West Nile virus, and hepatitis C. Some of these infections resulted in fatal outcomes up to 1 year following discontinuation of rituximab [116]. Most of these serious viral infections occurred in patients with hematologic malignancies receiving combination chemotherapy with rituximab.

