3.2.3 Secondary Safety Endpoints

The safety endpoints will include the following:

1. All NCI-CTCAE Grade 3-5 AEs, which are defined as possibly, probably, or definitely related to rituximab.
2. All NCI-CTCAE Grade 3-5 adverse events.
3. All infection related events.
4. Treatment-related mortality, defined as death occurring at any time after randomization and possibly, probably, or definitely resulting from treatment given in the study. Study investigators will make an initial determination of the cause of death of any subject and if uncertainty remains, a final decision will be made by an independent blinded panel after reviewing all clinical and, if available, autopsy data.
5. All-cause mortality, defined as any death occurring at any time after randomization.
6. CD19+ B cell levels post treatment (note that analyses will be performed regularly per Table 6.1 through 48 weeks and quarterly thereafter as documented in Protocol Section 3.1, *Description of Study Design*).
7. Peripheral blood cell counts, liver function, and creatinine levels after treatment.

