8.2. Adverse Events

All AEs will be classified by system organ class (SOC) and preferred term, according to a standardized thesaurus (Medical Dictionary for Regulatory Activities [MedDRA] version 13.1). The severity of AEs will be classified using the National Cancer Institute's (NCI's) Common Toxicity Criteria for Adverse Events (CTCAE) version. Each AE is entered on the electronic case report form (eCRF) once at the highest severity. As such, no additional data manipulation is needed to identify events.

Adverse events NCI-CTCAE grade 2 and above will be collected from the time the subject signs the informed consent until he/she initiates study intervention or until he/she is determined to be ineligible to receive study intervention, if the investigator determines that the adverse event is related to a study-mandated procedure, treatment, or change in treatment.

For all participants, adverse events NCI-CTCAE grade 2 and above will be collected from the time of initiation of study intervention (i.e., the administration of the first dose of study drug/study drug) until he/she completes study participation or until 30 days after he/she prematurely withdraws (without withdrawing consent) or is withdrawn from the study. During the quarterly monitoring period of the study, only NCI-CTCAE grade 3 and higher infections are collected on the adverse events CRF page. Grade 3 and higher infections that occur during the quarterly monitoring period will be listed separately and will not be included in data tabulations, unless otherwise specified.

Treatment-emergent AEs will be identified as those with an onset date on or after the first dose of study medication. If the start of the AE in relation to the start of study medication cannot be established (e.g., the start date for the AE is missing), then the AE will be considered treatment-emergent. All data tabulations will be of only treatment-emergent events unless otherwise specified; non-treatment-emergent AEs will be listed.

An overall summary table will be developed to report the number of events and the number and percentage of subjects having at least one event in the following categories:

- AEs
- AEs requiring 24-hour reporting to the sponsor
- AEs indicated as serious
- AEs that lead to study drug discontinuation
- AEs with an outcome of death
- AEs by relationship to a study drug
- AEs reported by maximum severity

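### SAP 8.3.2 stops treatment-related mortality before Week 48, against the protocol's open-ended definition, and so leaves out late fatal infections for which relationship is recorded

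*SAP*

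**What the plan says.** The protocol gives the definition twice. Section 3.2.3, item 4, has "Treatment-related mortality, defined as death occurring at any time after randomization and possibly, probably, or definitely resulting from treatment given in the study", and Section 8.3.1 has "Treatment-related mortality, defined as death occurring at any time after randomization and possibly, probably, or definitely resulting from study treatment". Neither sets an upper time limit. The SAP synopsis repeats the open-ended definition under its secondary safety endpoints.

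SAP 8.3.2 then narrows it: "Treatment-related mortality will be defined as death occurring after randomization and before Week 48". It explains that relatedness can be assessed only for deaths reported as SAEs, and that "relationship to study treatment was not collected for deaths recorded on the Post-Study Follow-Up/ Week 104 Vital Status CRF page". The endpoint is therefore summarised at Week 48 only, while all-cause mortality is summarised at Weeks 48 and 104.

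The same section says that a death after main-study completion is still reported as an SAE if the subject is in quarterly B cell monitoring and the cause is an infection of Grade 3 or higher. SAP 8.2 says that infections of that grade in the quarterly period "will be listed separately and will not be included in data tabulations", unless otherwise specified, and it plans a separate listing for them.

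Protocol 8.5.6 promises that major departures from the protocol will be noted in the SAP. SAP Section 11 lists three changes, and this is not among them.

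**The concern.** Treatment-related mortality is a pre-specified safety endpoint, and the SAP contradicts both the protocol and its own synopsis on its time span. The cut-off also excludes deaths for which the needed data exist.

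Those deaths are the kind that the protocol keeps watch for after Week 48. It continues surveillance for infections of Grade 3 or higher until B cells recover, or for two years after first treatment. Its risk section says of serious viral infections after rituximab: "Some of these infections resulted in fatal outcomes up to 1 year following discontinuation of rituximab". With 30 subjects per arm, a single related death would matter to how the safety profile is read. An analyst following SAP 8.3.2 as written would leave it out of the endpoint.

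**Working it through.** The documents give no expected number of treatment-related deaths, so there is no figure of the plan's to reproduce. The check is mainly a comparison of passages.

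**1. The definitions**
- Protocol 3.2.3 and 8.3.1: any time after randomisation.
- SAP synopsis: any time after randomisation.
- SAP 8.3.2: after randomisation and before Week 48.
- SAP Section 11: silent.

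**2. Does the SAP's reason cover what the cut-off removes?** Deaths after Week 48 fall into two groups.
- Deaths known only from the Week 104 check. Relationship is not collected, so the reason applies.
- Fatal infections of Grade 3 or higher in quarterly monitoring. SAP 8.3.2 says these are reported as SAEs. Protocol 7.3.5 puts SAEs on the AE form as well as the SAE form, and Protocol 7.4.2 has the site investigator record attribution on the AE form. Relationship is therefore available and the reason does not apply.

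**3. Tracing one case.** Take a subject with unrecovered B cells who dies at Week 60 of an infection judged possibly related.
- Included: all-cause mortality at Week 104, its Kaplan-Meier curves and log-rank test, the displays of time and cause of death, and the listing of quarterly-period infections.
- Not included: treatment-related mortality (SAP 8.3.2) or, unless otherwise specified, the AE tabulations (SAP 8.2).

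**4. The risk window in the protocol.** Section 1.4 places most PML diagnoses within 12 months of the last infusion. With that infusion at Week 2, the window ends at 2 + 52 = Week 54, which is 6 weeks past the cut-off.

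**5. Size.** The only mortality inputs are all-cause. Protocol 1.1 cites survival of "81%, 63% and 56% at 1, 2, and 3 years from diagnosis respectively". For 60 subjects:
- Deaths by Week 48: 60 × (1 − 0.81^(48/52)) = 10.6
- Deaths by Week 104: 60 × (1 − 0.63) = 22.2
- Difference: 22.2 − 10.6 = 11.6, and 11.6 / 22.2 = 52%

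Other readings of the survival figures change that share:
- Linear interpolation: 53%.
- Constant hazard at 50% one-year survival, the low end of the cited range: 37%.
- Entry 0.5 or 1 year after diagnosis: 44% or 33%.

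The range is 33–53%, all of it all-cause.

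To get from 11.6 to infection deaths reported as SAEs takes two shares that the documents do not give. Assume that 5–30% of late deaths are infections and that 25–100% of those subjects are in quarterly monitoring:
- Low: 11.6 × 0.05 × 0.25 = 0.1
- High: 11.6 × 0.30 × 1.00 = 3.5

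Only the part of these judged related would enter the endpoint.

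**The case against.** The SAP states its restriction and its reason openly in 8.3.2. Limiting attribution to the period when every death in an active subject is an SAE is defensible, and protocol 8.3.1 makes all safety comparisons exploratory. Late deaths are not lost, since they enter all-cause mortality, the death displays and the infection listing. Under Protocol 7.8.2, any PML or any unexpected related death triggers an emergency DSMB review, with no Week 48 limit stated. All of this stands. It limits the harm, but it does not explain why deaths with a recorded relationship are excluded, or why Section 11 omits the change.

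A reader might infer several stronger points that the documents do not support:
- **That about half of the relevant deaths are lost.** The 52% is a share of all-cause deaths, most of which would be expected to come from PAH itself. The survival figures run from diagnosis, while Protocol 4.1 allows entry up to five years later. On the same figures, deaths between Weeks 48 and 54 number about 60 × (0.823 − 0.802) = 1.3, again all-cause.
- **That late fatal viral infection is established for this population.** Protocol 1.4 goes on to say that most such infections were in haematologic malignancy with combination chemotherapy. It does describe PML in autoimmune disease as well.
- **That the cut-off also removes attribution for subjects who withdraw and die before Week 48.** That gap comes from the 30-day SAE rule in Protocol 7.3.5. Fatal infections of Grade 3 or higher during B cell follow-up can still be reported as SAEs.
- **That every death found at Week 104 could simply be attributed.** Protocol 6.5.4.13 allows vital status from public records or registries, which may lack the clinical detail. Protocol 3.2.3 provides for a blinded panel on uncertain causes but does not show that it would have such information.

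**Conclusion.** The point holds in a limited form. SAP 8.3.2 conflicts with the protocol and with the SAP synopsis, the change is not listed in Section 11, and the stated reason fails for fatal infections reported as SAEs during quarterly monitoring. Following the SAP as written, a related late fatal infection would be left out of a pre-specified safety endpoint while still being visible elsewhere in the report.

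The number of related deaths affected cannot be derived from the documents and is probably small. The 0.1 to 3.5 range is for all fatal infections in both arms and rests on assumed shares. The 33–53% range measures follow-up time after the cut-off in terms of all-cause deaths and should not be used as the size of this problem. A reader might also conclude that the report would claim no treatment-related deaths. That would require dropping the Week 48 label that SAP 8.3.2 attaches to the summary.

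**What to change.** In SAP 8.3.2:
1. Keep the Week 48 summary of treatment-related mortality.
2. Add a row, by arm, that also includes every later SAE-reported death judged possibly, probably or definitely related, including those in quarterly monitoring.
3. State that other deaths found at the Week 104 check have no attribution.
4. Reconcile the definition with the SAP synopsis and list the change in Section 11.

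The cost is SAP wording and one table row, from data already collected. The downside is that SAE capture after Week 48 is limited to subjects with unrecovered B cells, so it may differ by arm. The added row should be labelled descriptive and not read as a comparison between arms.
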